2.3 Benefit-risk assessment

This study is designed to contribute to the development of a multivariate algorithm to help haemodialysis patients monitor and manage their fluid intake. The Sixty device will collect data during multiple haemodialysis sessions allowing the algorithm to be trained to recognise different fluid states, from dry weight to varying degrees of fluid overload. Furthermore, the continuous monitoring in the interdialytic period will capture the “real world” data, and will be used to verify the validity of the algorithm.

The Sixty device prototype will not provide feedback to the patient so it is not expected that the study or the Sixty device will create any additional risks for haemodialysis patients. In the event of any technical problems with the device, the Sixty team will be available to provide technical support.

All patients will receive optimal haemodialysis during the study. In addition, the on-call nephrology registrar at Beaumont hospital will be available to handle any medical enquiries from patients enrolled in the study.

3. Description of design and trial population

[figure not shown]

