MAIN CRITERIA FOR INCLUSION	Age ≥ 18 years, demonstrated understanding of use of the Sixty device and home blood pressure monitor, written informed consent
TEST PRODUCT	Sixty wearable hydration monitor
COMPARATOR PRODUCT	None
END OF STUDY DEFINITION	3 weeks
PRIMARY ENDPOINT	Volume status measured by Sixty device compared to haemodialysis machine and bioimpedance data
SECONDARY ENDPOINTS	Acceptability of Sixty device
INTERIM ANALYSIS	None planned
STATISTICAL METHODS	Descriptive tables or figures will be prepared. Within-patient comparison of fluid status data as determined by different methodologies.

FLOW CHARTS

Flow chart 1 Assessments during observation period

	study observation period (3 weeks)				
	Baseline clinic visit	At each dialysis session	Week 1	Week 2	Week 3 (end)
Informed consent	X				
Demographic data (include dialysis & medicines history)	X				
Vital signs, body weight, routine hemodialysis measurements in-clinic ^A	X	X	X	X	X
Assess fluid status with bioimpedance ^B	X		X	X	X
Instruction/patient training on use of Sixty device	X				
Wear Sixty device daily ^C	X	X	X	X	X
Download data and recharge Sixty device ^D		X	X	X	X
Record symptoms related to fluid status ^E	X	X	X	X	X
Record adverse events ^F	X	X	X	X	X
Patient records blood pressure at home once/day ^G	once/day throughout study				
Stop using Sixty device ^H					X
Acceptability of Sixty device questionnaire ^I					X
End of study					X

^A Routine measurements (at each hemodialysis session) include total fluid removal, interdialytic weight gain (IDWG), proportion of haemodialysis sessions in which IDWG is $\leq 4\%$, pre-dialysis and post-dialysis weight, pre-dialysis, intradialytic and post dialysis BP and pulse rate.

^B Fluid status will be assessed by bioimpedance measurements immediately before start and immediately after end of haemodialysis.

^C Sixty is a wrist-worn hydration monitor. It uses optical spectroscopy and machine learning algorithms to determine hydration level. No data is displayed to the patient. The device should first be worn by the patient for five minutes before the haemodialysis session at the Baseline Visit and throughout that haemodialysis session. It should then be worn throughout the study observation period, including during all haemodialysis sessions.

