1.2 Product profile

The Sixty device is a wearable hydration monitor that is currently in development. Photographs of the current prototype and expected final designs are shown in Figure 1.2: 1.

Figure 1.2: 1: Photographs of prototype and expected final design of Sixty device

The prototype device (left-hand image) measures 66mm x 48mm x 10mm. The on/off button and charging port are visible on the top edge. The surface facing the camera will be in contact with the dorsal surface of the user's wrist. The expected final design is shown in the right-hand image. This is expected to be approximately the size of a commercially available smart watch (e.g. Apple watch).

The Sixty device uses diffuse reflectance spectroscopy to measure fluid levels subdermis. Optical sensors shine light of a specific wavelength onto the skin and the amount of light reflected back can be correlated to different body components (e.g. water). The machine learning algorithm is trained using a calibrated data set of known fluid states allowing the device to interpret the data and provide feedback on fluid status.

The prototype device used in this study does not reflect the final aesthetic or "looks like" design, but provides the necessary functionality to establish proof of principle in fluid overloaded patients. It is designed to be very simple to operate, with only one button to turn it on and off. The simple user interface indicates that the device is on/off and is functioning correctly. The prototype device will only collect data and does not provide feedback to the user on their hydration status. Data is collected locally on a memory card (i.e. SD card) which will be removed periodically to recover the data.

The device and battery is designed to run for an extended period and can be charged via a USB cable. Charging the device and collection of data will be coordinated at the haemodialysis study centre to minimise data gaps and to reduce unnecessary complexity for the patient.

Patent acceptability will be assessed.

2. Rationale, objectives and benefit-risk assessment

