2.2 Trial objectives

The objective of this pilot-scale study is to assess how the Sixty hydration monitoring device functions when used in a range of haemodialysis patients of varying age, gender, body habitus and volume status. Patients with a range of baseline fluid status (ranging from 15% above to 10% below their dry weight as determined by bioimpedance) will be considered for enrollment.

The primary objective is to determine the validity and reproducibility of the data captured by the Sixty device in haemodialysis patients. (The goal is to determine if the data captured by the Sixty device and the additional haemodialysis parameters described can be developed into algorithms that provide actionable insights to better manage fluid overload in the interdialytic period.)

Haemodialysis parameters will be assessed as usual during the study and will include:

- total fluid removal (each haemodialysis session)
- interdialytic weight gain (IDWG)
- proportion of haemodialysis sessions in which IDWG is $\leq 4\%$.
- pre-dialysis weight
- post-dialysis weight
- pre-dialysis blood pressure (BP)
- intradialytic BP

- post-dialysis BP
- number and type(s) of BP medications
- requirement for nursing interventions (e.g. stopping dialysis or administering fluid bolus)
- adverse events requiring or prolonging hospitalisation
- requirement for additional unscheduled dialysis

Fluid volume data measured by the Sixty device will be compared to recorded extracted fluid and volume status as measured by haemodialysis machine data and bioimpedance findings.

Patient-reported symptoms related to haemodialysis and the underlying medical condition will be recorded before haemodialysis. Symptoms data will be assessed and compared with fluid status data.

Data on BP measured once/day at home during the interdialytic period will also be recorded.

An additional objective of this observational study is to assess the acceptability and utility of the Sixty device (from the patient perspective).

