5.1 Efficacy

5.1.1 Efficacy endpoints

5.1.1.1 Primary endpoint

The primary endpoint will be to evaluate the accuracy of the Sixty device data in assessing volume in haemodialysis patients compared to gold standard monitoring techniques. The volume status as measured by the Sixty device will be compared with volume status as measured by bioimpedance, patient symptoms, and traditional haemodialysis parameters.

The primary endpoint variables include:

Comparison of volume status as measured by Sixty device compared to bioimpedance pre- and post-dialysis:

- volume overload as defined by bioimpedance: overhydration (OH)/extracellular water (ECW) > 15% (corresponding to 2.5L)
- normohydration defined as: ECW -6 to + 6% (corresponding to -1.1L to + 1L)

Correlation of volume status with patients' symptoms before haemodialysis based upon the symptom score developed by Kraemer et al⁸.

Symptoms of hypovolaemia:

- thirst directly after haemodialysis
- symptomatic hypotension, on change of position
- symptomatic hypotension
- nausea and vomiting
- muscle cramps
- limpness/ tiredness between dialysis sessions
- dizziness between dialysis sessions

Symptoms of hypervolaemia

- chronic coughing (new)
- dyspnea on recumbency
- dyspnea at rest; 1 pillow
- dyspnea at rest: 2 pillow
- dyspnea at rest: 3 pillows
- pretibial oedema
- paroxysmal nocturnal dyspnea (PND)

Correlates of volume status as measured by haemodialysis parameters including:

- total fluid removal (each haemodialysis session)
- IDWG
- proportion of haemodialysis sessions in which IDWG is $\leq 4\%$.
- pre-dialysis and post-dialysis weight
- pre-dialysis, intradialytic and post dialysis BP
- pulse rate
- requirement for nursing intervention such as stopping dialysis or administering fluid bolus
- adverse events including, but not limited, to muscle cramps, symptomatic hypotension, access-related complications, hypertension-related symptoms, congestive heart failure, pulmonary edema, requirement for additional unscheduled dialysis, or need for hospitalisation
- number and type(s) of BP medications
- home BP measured once/day during the interdialytic period

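### Section 2.3 trains an algorithm on this study's dialysis sessions and verifies it on interdialytic data from the same 20 patients, so the verification cannot speak for new patients

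*Protocol*

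**What the plan says.** Section 2.3 (Benefit-risk assessment) sets the purpose: "This study is designed to contribute to the development of a multivariate algorithm to help haemodialysis patients monitor and manage their fluid intake". It then gives a scheme in two steps. Training: "The Sixty device will collect data during multiple haemodialysis sessions allowing the algorithm to be trained to recognise different fluid states". Verification: continuous monitoring between sessions "will be used to verify the validity of the algorithm".

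Three other places bear on which algorithm is meant.

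- Section 2.2 asks whether the Sixty data together with the haemodialysis parameters "can be developed into algorithms that provide actionable insights to better manage fluid overload in the interdialytic period".
- Section 1.2 says of the device itself: "The machine learning algorithm is trained using a calibrated data set of known fluid states". The source and date of that data set are not given. The same section says: "The prototype device will only collect data and does not provide feedback to the user on their hydration status".
- Flow chart 1, footnote C, says of the device: "It uses optical spectroscopy and machine learning algorithms to determine hydration level".

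The primary endpoint (5.1.1.1) includes "Comparison of volume status as measured by Sixty device compared to bioimpedance pre- and post-dialysis", and 7.3.1 repeats the comparison against bioimpedance, machine data and symptoms. Sections 3.1.1 and 4.1.2 give one centre and one observation sequence for every patient, and 7.6 gives n = 20. Under 8.3.3 the device developer receives the haemodialysis, bioimpedance and symptom data as well as the Sixty data.

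**The concern.** Repeated readings from one patient resemble each other. A model fitted to some readings of a patient can partly learn that patient's own level, and it will then look accurate on that patient's other readings without having learned anything that transfers. Splitting by period leaves this in place; splitting by patient removes it.

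The verification period also has little reference of its own. Bioimpedance is taken only around dialysis, so an interdialytic interval has a volume reference only at its ends, and those ends belong to sessions that supply the training data. In between there is home blood pressure once a day.

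At stake is what the pilot can claim. Validity is the primary objective (2.2), and the study is to show whether the approach has merit (2.1). There is no hypothesis (7.2) and the analysis is descriptive (7.3), so the reported agreement is itself the evidence.

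**Working it through.** The plan has no figure of its own to reproduce: n = 20 is stated to be arbitrary (7.6).

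**Step 1. Readings available.** Inputs: 20 patients (7.6), bioimpedance on 4 occasions (section 6), before and after dialysis (footnote B). 20 × 4 × 2 = 160 readings from 20 independent patients. The count is not firm: the wording in 6.3.1, 6.3.3 and 6.3.4 could be read as four readings per session (20 × 4 × 4 = 320), and 8.5 allows a lower recruitment target.

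**Step 2. References for interdialytic intervals.** About 3 sessions a week for 3 weeks (6.1) gives 9 or 10 sessions, hence 8 or 9 intervals, per patient. The session numbers of the weekly visits are assumed.

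| Sessions | Bioimpedance at | Intervals | One end | Both ends | Neither |
|---|---|---|---|---|---|
| 10 | 1, 4, 7, 10 | 9 | 6 | 0 | 3 |
| 9 | 1, 3, 6, 9 | 8 | 6 | 0 | 2 |

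For 20 patients: 20 × 6 = 120 of 20 × 9 = 180 intervals, or 120 of 20 × 8 = 160, have bioimpedance at one end and none has it at both. Interdialytic weight gain is recorded at each session and so covers every interval.

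**Step 3. Which algorithm.** In 2.3 the algorithm to be trained refers back to the multivariate algorithm of the paragraph's opening sentence. Section 2.2 treats algorithms as something to be developed from Sixty data plus dialysis parameters. Section 1.2 describes the device's own algorithm separately. These favour a later product. Against that, footnote C makes the Sixty value algorithm-derived, the prototype only collects data, and no section says which version yields the primary value. The second reading is open but nowhere affirmed.

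**Step 4. Possible size (illustration only).** Assumed: least squares; 5 to 40 features; within-patient correlation of features/fluid 0/0, 0.3/0.3 or 0.7/0.5; 20 patients × 8 training readings. Entries are mean correlations between fitted and reference value, ranging over 5 to 40 features.

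| Raw levels | 0/0 | 0.3/0.3 | 0.7/0.5 |
|---|---|---|---|
| No signal: readings used to fit | 0.17–0.50 | 0.21–0.57 | 0.31–0.72 |
| No signal: same patients, other readings | about 0 | 0.09–0.17 | 0.24–0.48 |
| No signal: new patients | about 0 | about 0 | about 0 |
| One feature with true r 0.5: readings used to fit | 0.52–0.66 | 0.53–0.70 | 0.55–0.79 |
| Same, other readings of same patients | 0.35–0.48 | 0.46–0.50 | 0.53–0.63 |
| Same, new patients | 0.35–0.48 | 0.33–0.47 | 0.28–0.42 |
| Same, leave-one-patient-out | 0.33–0.46 | 0.30–0.43 | 0.25–0.35 |

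For the change from post-dialysis to the next pre-dialysis reading (400 readings, both ends used in training, 9 intervals per patient):

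| Change | 0/0 | 0.3/0.3 | 0.7/0.5 |
|---|---|---|---|
| No signal: in-sample | 0.11–0.32 | 0.05–0.19 | 0.02–0.15 |
| No signal: patients held out | about 0 | about 0 | about 0 |
| True r 0.5: in-sample | 0.51–0.57 | 0.48–0.50 | 0.33–0.38 |
| True r 0.5: patients held out | 0.43–0.50 | 0.39–0.48 | 0.27–0.36 |

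So same-patient verification of raw levels is harmless when readings within a patient are uncorrelated and clearly optimistic when they are strongly correlated. Change removes stable patient differences. With a true signal and 5 or 10 features its optimism is only 0.01 to 0.04 (for example 0.51 − 0.50 and 0.51 − 0.47 at 0/0); with 40 features it reaches 0.57 − 0.43 = 0.14.

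**The case against.** A reader might infer that the primary accuracy result will be in-sample. The documents do not support that as a finding. The natural reference of the algorithm in 2.3 is the multivariate product, 2.2 supports a later development, and 1.2 describes the device algorithm apart from it. Training and verification appear in no endpoint and no planned analysis. This stands, and the in-sample reading is kept only as one that the text leaves open.

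It can also be said that hold-out rules and version locking belong in an analysis plan that is not shown. That is fair for the detail. But 2.3 is not silent: it states a scheme, and the split it states is by period within one cohort. An analysis plan that added a patient-level split would be correcting that scheme.

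A third point is that references do exist. Interdialytic weight gain and home blood pressure are listed among the primary endpoint variables in 5.1.1.1. That stands: the sentence in 2.3 names no reference, but the study collects a usable one.

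Finally, the sizes above depend on assumed features, correlations and fitting method, and range from no optimism to a large one. That also stands; they show direction and possible size and are not an estimate for this device. The study is also only to contribute to the algorithm's development, so other training data may be added.

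**Conclusion.** The concern holds in a limited form. Followed as written, section 2.3 yields a verification that is not independent at patient level and cannot show that the algorithm works in new patients. This rests on the text alone: one centre, one sequence, one cohort, split by period.

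On the more natural reading the primary comparison is untouched, and the harm is confined to the claim that a later algorithm was verified. If instead the algorithm trained here produced the primary Sixty value, that accuracy would be in-sample and biased upward. The protocol should close off this possibility; it does not state it.

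Any optimism lies between none and substantial for raw levels in the same patients and is smaller for interdialytic change, under the assumptions listed. Severity is minor to moderate: a descriptive pilot with no hypothesis test and an arbitrary sample size.

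**What to change.** 1. In 2.3 and 7.3.1, state that the primary comparison uses a device algorithm not trained on this study's reference data. If it is trained on them, report accuracy only from predictions in which all readings of a patient are held out together, for example leave-one-patient-out, and not from the in-sample fit.
2. For the algorithm that 2.3 trains, replace the same-patient verification by a comparison of the device's change from post-dialysis to the next pre-dialysis reading with the recorded interdialytic weight gain, with patients held out (160 to 180 intervals at full recruitment). Otherwise describe the step as exploring the algorithm and drop the claim to verify its validity.

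The cost is protocol wording and some refitting (20 fits for leave-one-patient-out). No patients, visits or measurements are added. The accuracy figure will look less favourable than an in-sample one and is slightly pessimistic with 20 patients: in the illustration with a true r of 0.5, leave-one-patient-out lies 0.02 to 0.08 below the fitted model's own correlation in new patients.

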3.1 Overall design and plan

Prospective, open-label run-in observation period with Sixty device (3 weeks).

The study will not make any changes to the usual haemodialysis schedule for the patients.

A diagram of the trial design is shown on Figure 3.1: 1 below.

Figure 3.1: 1 Diagram of trial design

3.1.1 Administrative structure of trial

This is a single centre study at the Beaumont Hospital, a tertiary care centre for nephrology in Dublin, Ireland.

The Sixty hydration monitor was developed and is owned by Design to Value Ltd, Innishannon, Cork, Ireland.

The study is being conducted as part of the Haemodialysis Outcomes & Patient Empowerment (HOPE) project supported by the Disruptive Technology Innovation Fund of Ireland (DTIF). The HOPE project is a collaboration between the Royal College of Surgeons in Ireland, Beaumont Hospital, patientMpower Ltd., Digital Depot, Dublin and Sixty (registered as Design to Value Ltd.), Innishannon, Co. Cork. The objective of HOPE is to develop artificial intelligence-enabled software to improve determination and maintenance of fluid balance in haemodialysis patients with a long-term goal of increasing the proportion of patients receiving dialysis at home. This study is a collaboration between all partners in HOPE and the data and outcomes will be shared with all partners. The study is funded by the DTIF.

The protocol was designed by [name] [name] (Principal Investigator), [name] (both of Beaumont Hospital, Dublin 9, Ireland), Design to

Value Ltd, Innishannon, Co. Cork, Ireland and patientMpower Ltd., Digital Depot, Dublin 8, Ireland.

3.2 Discussion of trial design, including choice of control group

This is a pilot-scale, prospective, open-label, single-arm observational study.

All patients will be allocated to the same observation sequence.

Patients will follow their usual haemodialysis regimen throughout the study. Patients' dry weight will be optimised using gold standard care (bioimpedance measurements) during the study.

Clinical assessments (e.g. IDWG, BP, pulse rate, ultrafiltration volume, symptoms) will be assessed at each dialysis visit.

The trial design will allow assessment of the validity and reproducibility of data collected by the Sixty device in haemodialysis patients. Data from the Sixty device will be compared against other validated methods of volume assessment (haemodialysis machine and bioimpedance data) and with observed symptoms in patients across a range of age, genders and volume status.

The study will also allow evaluation of the utility and acceptability of the Sixty device in a haemodialysis patient population. This will be assessed from the patient perspective.

3.3 Selection of trial population

3.3.1 Main diagnosis for study entry

Require maintenance haemodialysis in an ambulatory care setting.

Patients with a range of baseline fluid status (ranging from 15% above to 10% below their dry weight as determined by bioimpedance) will be considered for enrollment.

3.3.2 Inclusion criteria

Aged at least 18 years

Demonstrates understanding of correct use of the Sixty device.

Capable and willing to measure blood pressure at home on a daily basis.

Willing to give written informed consent.

3.3.3 Exclusion criteria

Conditions precluding accurate use of bioimpedance (e.g. limb amputations, severe malnourishment).

Significant confusion or any concomitant medical condition, which would limit the ability of the patient to record symptoms or other parameters.

3.3.4 Removal of patients from therapy or assessments

3.3.4.1 Removal of individual patients

Patients are free to withdraw from the study at any time without any impact on their ongoing medical care.

The investigator may withdraw a patient from the study at any time if they believe that further participation in the study is not in the best interests of the patients.

3.3.4.2 Discontinuation of the trial

The study may be terminated early if recruitment is significantly behind schedule or if for any other reason, it is unlikely that the study can be completed.

4. Study observational intervention

All patients will continue to receive their usual haemodialysis regimen throughout the study as prescribed by their healthcare professionals.

4.1 Observational intervention to be assessed

4.1.1 Identity of observational intervention and comparator(s)

The Sixty device is a wearable hydration monitor that is currently in development. It uses diffuse reflectance spectroscopy to measure fluid levels subdermis. Optical sensors shine light of a specific wavelength onto the skin and the amount of light reflected back can be correlated to different body components (e.g. water). The prototype device used in this study provides the necessary functionality to establish proof of principle in fluid overloaded patients. This prototype device will only collect data and will not provide feedback to the user on their hydration status.

There is no comparator intervention.

